Skin aging is a complex biological process mainly influenced by two independent mechanisms, intrinsic and extrinsic skin aging [1]. Intrinsic skin aging is determined primarily by inherent genetic factors, hormonal status, cellular metabolism and function [2]. It represents degenerative aging processes seen in other organ systems as a consequence of the passage of time. Extrinsic skin aging results from various external influences including solar UV radiation, health and lifestyle factors, such as tobacco smoking, environmental pollution, and other systemic conditions, such as diabetes and renal insufficiency [3-5].

In skin with chronic exposure to UV radiation, termed photoaging, alterations in skin structure and function depend primarily on the degree of sun exposure and baseline skin pigment. UV radiation induces collagen breakdown. Diminution of collagen framework that supports vascular plexus within the skin leads to broken vessels [8]. The Langerhans cell population representing immune system of the skin is found to be reduced after chronic exposure to UV radiation contributing to impaired immune response to antigen and skin cancer cells [6,7].

These age-related changes caused by chronic sun exposure have not been well-documented in the lips [10]. The majority of literature on the aging lip has focused on volume loss. Hyaluronic-acid based fillers have been used primarily for volume augmentation, but their effect on lip color and texture has seldom been defined [9,12].

We propose to study aging of the cutaneous changes of human skin anatomy in the lips and perioral area to better understand and quantify the aging process in this, including the effect of age on lip redness.

We also aim to test the effects of a common lip augmentation procedure, hyaluronic-acid based fillers, on the appearance of aging lips, in addition to the tolerability of this procedure. We hypothesize that dermal lip fillers may decrease the redness of the lips.

Besides, we want to evaluate oxytocin level changes and relate it to subjects' satisfaction with procedure.

The study will take place at MGH's Clinical Unit for Research Trials & Outcomes in Skin (CURTIS) at [name] or Translational Clinical Research Center (TCRC) on the 12th floor of the White Building.

III. Specific AIMS

To:

- Compare the changes in skin anatomy due to intrinsic aging
- Correlate clinical assessment with OCT imaging;

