- Compare changes in lip color, texture and volume before and after filler with non-invasive imaging, including digital photography, OCT and three-dimensional imaging
- To assess the tolerability of lip filler by evaluating pain level from lip filler treatment at initial insertion and overall procedural pain
- To evaluate how oxytocin levels change during and after an aesthetic procedure.
- To assess lip color change after the procedure.
- To evaluate patient satisfaction related to the procedure.

IV. SUBJECT SELECTION

Subjects will be screened to determine if they meet all the eligibility criteria specified below. We will recruit and screen up to 50 subjects with the goal of 40 subjects enroll and complete the study (20 per study arm).

a. Inclusion Criteria

1. Subjects must be able and willing to provide written informed consent and comply with the requirements of the study protocol;
2. In good general health, based on answers provided during the screening visit;
3. Subjects must be able to read and understand English;
4. Female subjects;
5. Aged 21-30 years and Post menopausal women;
6. Skin Types (Fitzpatrick Skin Phototypes I-VI);

* Smoking history is self-report.

7. Have very thin to moderately thick lips (Lip Fullness Grading Scale [LFGS] scores 0–2).

b. Exclusion Criteria

1. Participation in another investigational drug or device clinical trial in the past 30 days;
2. Are pregnant or lactating;
3. Intake of hormone replacement therapy (HRT) in the past 6 months;
4. Have a history of drug or alcohol abuse or have reported habitual alcohol intake greater than 2 standard drinks per day [e.g., 2 beers, 2 glasses of wine, or 2 mixed drinks];
5. Presence of eczema, psoriasis, or any other skin disease on the lips or perioral skin;
6. Have birth marks, tattoos, scars, or any other disfiguration of the skin in the skin area of interest;
7. Use of any anti-aging skin care products containing retinoic acid, retinol, or other retinoids (e.g. tazarotene, adapalene) or estrogen on the skin area of interest in the past 6 months;
8. Use of any prescription topical medication, such as corticosteroids or hydroquinone on the skin area of interest in the past 6 months;
9. Have a history of photodynamic therapy treatment or any skin rejuvenation procedure on the skin area of interest;
10. History of blood-clotting abnormality;
11. History of keloid formation or hypertrophic scarring;

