- Three-dimensional imaging using the Cherry Imaging system (before and after the procedure)
- Digital photography of the lips and perioral area

Filler treatment of the lips with Restylane Kysse (if the subject has completely inverted lips the lip filler procedure will be optional and only imaging will be collected in visit 1)

- Lip volume assessment with Lip Fullness Grading Scale
- Subjects will be instructed how to report a pain score for first needle insertion and overall procedural pain. A visual 10 point pain scale will be used.

Wong-Baker FACES® Pain Rating Scale

©1983 Wong-Baker FACES Foundation. www.WongBakerFACES.org
Used with permission. Originally published in *Whaley & Wong's Nursing Care of Infants and Children*. ©Elsevier Inc.

- Intravenous access will be placed to facilitate four blood draws to analyze serum oxytocin levels, all of which will occur on Visit 1 as follow: after photography and OCT, and before the filler procedure starts, immediately after the filler procedure, after the “mirror reveal” (when we show the lips to the subject using a mirror) minutes and 30- 35 minutes after the filler procedure has been concluded.
- The questionnaires: “FACE-Q™ – satisfaction with outcome” and other questions will be applied right after the procedure to evaluate subject’s satisfaction and about lip color and shape changes.
- Documentation of Adverse Events
- Video recording (15-30 seconds-video) from subjects’ face and lips after the lip filler procedure. The video recording is optional.
- Upon completion of all treatments, the subject will be provided with aftercare instructions, remuneration and parking voucher if needed

Follow-up Call (3-7 days after Visit 1, 30 minutes)

Study staff will call the subject 3-7 days after Visit 1 to check-in and inquire about any post-procedure pain or any side effects. If there are any negative side effects from treatment, they will be evaluated and treated in accordance with standard medical procedures.

Visit 2 (2 weeks after Visit 1, 1 hour)

Subjects will be asked to return 2 weeks after Visit 1. Visit 2 is expected to last up to 1 hour. The following procedures and evaluations will be performed:

- Three-dimensional imaging using the Cherry Imaging system
- OCT imaging for microvasculature
- Digital photography of the lips and perioral area
- Lip volume assessment with Lip Fullness Grading Scale (LFGS)
- Documentation of adverse events

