A DSLR camera will be used to take images of the lips and perioral area before the dermal filler procedure takes place during visit 1 and then at the second study visit. Subjects will be asked to stand with limited facial expression so that consistent, photographic images can be obtained.

Video Recording

Study's encrypted Iphone 12 (no chip inside, used only for the study) will be used by study staff (investigator or research coordinators) to take a video recording from the subjects' face/ reaction during the "mirror reveal". From 15 to 30 seconds of video recording will be taken from subject's face after a mirror is used to show them their "new lips". This will happen after the dermal filler procedure takes place during visit 1. This video will be optional and subjects will express if they allow this video recording or not in the consent form. Subject's reaction after the "mirror reveal" will be correlated to Oxytocin levels.

Restylane Kysse Lip Filler Treatment

After the OCT imaging, Cherry Imaging and digital photography, Restylane Kysse lip filler will be injected into the submucosal layer of the lips and subcutaneous layer of the perioral area. This hyaluronic acid filler formulation contains local anesthetic lidocaine so no topical anesthetic will be applied. The subject will be positioned in a seated position and the treatment area will be cleaned prior to injection. One syringe with 1mL will be injected to lips and perioral area in accordance with standard aesthetic lip filler practices. We aim to inject the full amount of one syringe, but upon the investigators discretion we may inject +/- 0.25mL as needed. The area will then be gently massaged with Vaseline to ensure the dermal filler gel is distributed evenly [9]. The subject will experience sharp pain and mild pressure from initial injection, which will subside with subsequent insertions as the lidocaine numbing takes effect. Standard of care for aesthetic lip filler treatment will be followed.

Blood Draw

Four blood draws to analyze serum oxytocin levels, all of which will occur on Visit 1 as follow:

- After photography and OCT, and before the filler procedure starts, an intravenous access will be placed and approximately 3 cc of blood will be drawn into EDTA tubes containing Aprotinin supplied by the Brigham Research Core lab.

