- Immediately after the filler procedure, approximately 3 cc of blood will be drawn into EDTA tubes containing Aprotinin supplied by the Brigham Research Core lab.
- after the after the "mirror reveal" (when we show the lips to the subject using a mirror approximately 3 cc of blood will be drawn into EDTA tubes containing Aprotinin supplied by the Brigham Research Core lab.

- 30-35 minutes after the filler procedure has been concluded, a final approximate of 3 cc of blood will be drawn into EDTA tubes containing Aprotinin supplied by the Brigham Research Core lab.

Each sample will be allowed to clot for 30-60 minutes at room temperature to prepare serum, then centrifuged at 1600 x g for 15 minutes at 4°C by study staff, and the serum will be transferred to plastic tubes.

The samples will be placed on dry ice and hand-delivered by the research staff to the Brigham Research Core lab or stored at -80 degrees freezer located at the MGH Navy Yard in the [name] lab when immediate delivery is not possible.

The Brigham Research Core lab will process the ELISA assay to evaluate oxytocin levels.

e. Data to be collected and when data is collected

Study data will be collected during each study visit. Study data to be collected includes OCT imaging (various images as described above, visit 1 and 2), digital photography and Cherry Imaging of the lips and perioral area (visit 1 and 2), visual assessment of treated area (visit 2), video recording (optional) from subject's reaction after the mirror reveal, Lip volume assessment with Lip Fullness Grading Scale (screening visit, visit 1 and 2), pain assessment of initial injection and overall procedure (visit 1), blood samples (visit 1) and satisfaction questionnaire answers (visit 1 and 2). Medical history and medications will be documented at visit 1. There are no other biological data or health information to be collected in this study.

Information about side effects in the treatment area or any adverse events will be collected during the follow-up call and visits.

f. Remuneration

Subjects will be paid \$50 for completing all imaging activities and filler treatment during visit 1, and \$100 for completing visit 2. The total remuneration amount is \$150 upon completing the study. We will provide a parking voucher at MGH main campus for each visit upon request.

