OCT imaging is performed using the commercially available spectral-domain OCT scanner TELESTO II (Thorlabs Inc., Newton, New Jersey). It operates at a central

wavelength of 1,300 nm with a maximum output power of less than 10 mW. Using a lens with an optical lateral resolution of 13 μm (LSM03, Thorlabs Inc.), we acquire images with an oversampling factor of 2 \times leading to voxel sizes of $6.5 \times 6.5 \times 3.5 \mu\text{m}^3$ and a field-of-view (FOV) of $6 \times 6 \times 3.5 \text{ mm}^3$ (length \times width \times depth), acquired at an A-Scan rate of 76 kHz.

The imaging data is further processed and analyzed by custom made software tools implemented in MATLAB 2016b (MathWorks Inc). All OCT image data files will be labeled with the study subject number assigned to each subject upon consent. No identifying information will be used in labeling the image data files and the files will be stored on Partners OneDrive.

With angiographic image post processing, the capillary layer, typically in between 70 – 400 μm depth in skin, is displayed and converted to 2-dimensional images as maximum intensity projections. These 2-dimensional images are further segmented by an automatic, customized software and quantitative metrics such as vessel area, vessel length, vascular network complexity (fractal dimension) and vessel curvature are assessed. These characteristics of the capillary network are further used for inter- and intra-cohort investigations.

Cherry Imaging Photography Analysis

The Cherry Imaging analysis software contains distinct algorithms that process the generated three-dimensional images to calculate volume in cubic centimeters, precise color using saturation and hue, roughness detecting local variations in height/depth, and a ruler function that measures the distance between two distinct points. These will all be employed to analyze photos of lips, lip redness, roughness and volume.

DSLR Camera Photography Analysis

Standard photographs will be blindly reviewed by a physician and assessed using the Lip Fullness Grading Scale and Global Aesthetic Improvement Scale.

Video Recording

Videos will be blindly reviewed by a physician and assessed using the following grading scale (this grading scale is based on the model of answers that are given to subjects in the questionnaire):

Very satisfied	Somewhat satisfied	Somewhat dissatisfied	Very dissatisfied
----------------	--------------------	-----------------------	-------------------

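### The Background relates oxytocin change to subjects' satisfaction, but the only association the plan states uses the mirror-reveal reaction, scored by a physician from an optional video; the questionnaire answers are not named.

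*Combined protocol and SAP*

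**What the plan says.** - **Intent.** Section II (Background): "we want to evaluate oxytocin level changes and relate it to" subjects' satisfaction with the procedure. Section III (Specific Aims) lists the two topics separately: "To evaluate how oxytocin levels change during and after an aesthetic procedure" and "To evaluate patient satisfaction related to the procedure".
- **Oxytocin data.** Sections VI.a and VI.d (Blood Draw) schedule four draws at Visit 1: before the filler, immediately after it, after the mirror reveal, and 30-35 minutes after the procedure ends.
- **Subject's own satisfaction.** FACE-Q satisfaction with outcome and other questions are given right after the procedure at Visit 1 and again at Visit 2 (VI.a, VI.e). They are not described as optional.
- **Stated association.** Section VI.d, Video Recording: the subject's reaction after the mirror reveal "will be correlated to Oxytocin levels". No coefficient, draw or change score is named.
- **Scoring of the reaction.** Section VII.b, Video Recording: "Videos will be blindly reviewed by a physician and assessed using the following grading scale". The scale has four categories, from very satisfied to very dissatisfied, and is modelled on the questionnaire's answer options.
- **Optional status.** Section VI.d: "This video will be optional and subjects will express if they allow this video recording or not in the consent form". VI.a repeats it: "The video recording is optional".
- **Analysis section.** The oxytocin paragraph in VII.b covers only the assay. VII.c promises descriptive statistics and mentions neither oxytocin nor satisfaction.

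**The concern.** The purpose stated in the Background concerns what the subject herself feels about the result. The plan collects that directly, on the same day as the blood samples, yet names no analysis that joins the two. The association it does name replaces self-report with an observer's reading of a 15-30 second clip, available only for subjects who agreed to be filmed.

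Two things are at stake. First, a proxy that agrees imperfectly with the subject's own view weakens whatever correlation exists, even if everyone is filmed. Second, each refusal reduces an already small sample. There is also a reporting risk. With two satisfaction measures, four draws and no named main analysis, the pairing to report can be chosen after the data are seen.

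**Working it through.** **Matching intent to analysis.** Reading the sections together:

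| Element | Background intent | Only stated association |
|---|---|---|
| Oxytocin | change in level | levels, no draw or change named |
| Satisfaction | the subject's | reaction at the mirror reveal |
| Scored by | not stated; FACE-Q is collected | physician, four categories, from video |
| Who contributes | not stated | subjects who agreed to video |

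The step from reaction to physician's rating comes from reading VI.d with VII.b. No other scoring of the reaction is described.

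**Inputs for size.** From the documents: a goal of 40 completers, 20 per group (section IV). There is no plan figure to reproduce, because the documents give no correlation, alpha, power or video uptake. Assumed: true correlation r = 0.40, two-sided alpha 0.05, video uptake of 100%, 70% or 50%, and a correlation k of 0.8 or 0.6 between the physician's rating and the subject's own.

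**Effect of sample size.** Fisher z interval: tanh(atanh(r) ± 1.96/√(n − 3)). Approximate power: Φ(atanh(r)·√(n − 3) − 1.96). With atanh(0.40) = 0.4236:

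| Filmed | n | 1.96/√(n − 3) | 95% CI at r = 0.40 | Power |
|---|---|---|---|---|
| 100% | 40 | 0.322 | 0.10 to 0.63 | 73% |
| 70% | 28 | 0.392 | 0.03 to 0.67 | 56% |
| 50% | 20 | 0.475 | -0.05 to 0.72 | 42% |

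**Effect of the proxy.** If the rating is linked to oxytocin only through the subject's own satisfaction, the expected correlation is k × r.
- k = 0.8: 0.8 × 0.40 = 0.32; power 52% at n = 40 and 28% at n = 20.
- k = 0.6: 0.6 × 0.40 = 0.24; power 32% at n = 40 and 17% at n = 20. The 95% CI is -0.08 to 0.51 at n = 40 and -0.23 to 0.62 at n = 20.

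**Effect of selection through prior traits.** Assume normal variables, a willingness to be filmed that correlates 0.5 with later satisfaction, and filming of those above a cut-off. Truncation leaves willingness with variance 0.535 (75% filmed) or 0.363 (50% filmed). The variance of satisfaction among those filmed is v = 1 − 0.25 × (1 − that variance), which is 0.884 or 0.841. The correlation becomes 0.40·√v / √(0.16·v + 0.84), which is 0.38 or 0.37. The bias is small beside the interval widths above.

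**Upper bound on n.** VI.a makes filler optional for subjects with completely inverted lips and collects only imaging from them at Visit 1. Such subjects would have neither blood samples nor a Visit 1 FACE-Q, so 40 is a ceiling for the video and the questionnaire analysis alike.

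**The case against.** The strongest reply is that silence is not exclusion. The sentence in VI.d describes a procedure and does not claim to be the only or main oxytocin analysis. The Background names subjects' satisfaction, and the questionnaires are the only self-report of it, so they may well be meant to serve that purpose. The link appears in Background and not in the Specific Aims. The filmed reaction also has a rationale of its own: one draw is timed to the mirror reveal, and the video scale borrows the questionnaire's categories.

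Much of this stands. The documents do not show that the questionnaire was rejected for this purpose, only that no section assigns it. The video correlation is a legitimate secondary question. But a reader following the plan as written would run one oxytocin association, and it would not be the one in the Background.

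A reader might also infer that women pleased with their new lips are the ones who agree to be filmed, so that the correlation is biased by the outcome. The documents do not support that. Permission is recorded in the consent form, and V.a and V.b place consent before any study procedure, so no subject has seen her result. Only earlier traits could link willingness to satisfaction. Nor do the documents show that subjects are in fact lost, since no uptake is stated, or that every enrolled subject will have a FACE-Q score.

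**Conclusion.** The mismatch holds on the text: a stated intent about subjects' satisfaction, a stated association that rests on a physician's rating of an optional video, and no stated use of FACE-Q with oxytocin. The certain consequence is a proxy in place of a direct measure that is already collected. The conditional consequence is a smaller sample, anywhere from no loss upward.

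On the assumed values, halving the sample moves the lower confidence limit from 0.10 to -0.05, and a proxy agreement of 0.6 reduces 0.40 to 0.24 at any sample size. The true correlation, the uptake and the agreement are all assumptions, so these figures illustrate scale and do not predict results. Selection bias is probably modest and should not carry the argument. The objective is exploratory and the plan descriptive, but the correction is cheap and should be made before the data are analysed.

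**What to change.** In VII.c, state the following.

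1. The main oxytocin-satisfaction analysis is a rank correlation with 95% CI between the Visit 1 FACE-Q satisfaction score and one pre-specified oxytocin change, for example the post-mirror-reveal draw minus the pre-procedure draw.
2. It uses all subjects who had filler and have samples (at most 40), by cohort and combined with adjustment for cohort.
3. FACE-Q timing at Visit 1 is fixed relative to the mirror reveal. VI.a says only that it follows the procedure.
4. The video-rating correlation is secondary. Report how many subjects were filmed, and compare filmed and unfilmed subjects on FACE-Q and oxytocin.

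The cost is wording in the analysis section and one line on questionnaire timing. No new data are needed.

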The IV access can cause pain during its placement and any infection, thrombophlebitis or other adverse outcome will be treated according to standard medical care and recorded in the Adverse Event Log.

b. Drug side effects and toxicities

Possible side effects of Restylane Kysse dermal filler include redness (very common)*, pain/tenderness (very common), swelling (very common), lumps/bumps (very common), bruising (very common), itching (very common), or discoloration (very common). Potential risks included allergic reaction (rare but serious), infection (rare but serious), scarring (rare but serious), skin ulceration (rare but serious), ischemia (rare but serious), infarction (rare but serious) or change in skin tone (very common) [9].

Dermal fillers in the lips and perioral area are considered to be low risk but rare instances of localized skin necrosis are possible. In this case, if there are symptoms of occlusions, intense pain, or purple patches upon injection, we will have hyaluronidase (FDA approved for vascular occlusion necrosis) available in clinic.

A subject could have an allergic reaction to glycerol, Tegaderm or dermal filler (rare but serious). In this case, the allergic reaction would be recorded in the Adverse Events Log and would be monitored and treated by study staff in accordance with standard medical procedures.

*Please refer to the National Cancer Institute frequency categories listed below for reporting of possible side effects:

- a. Very Common (more than 1 out of 10 people)
- b. Common (between 1 and 10 out of 100 people)
- c. Uncommon (between 1 and 10 out of 1,000 people)
- d. Rare but Serious (less than 1 out of 1,000 people)

c. Device complications/malfunctions

Telesto II OCT imaging device (Thorlabs, Newton, NJ)

The Telesto II system is controlled and triggered by an external PC workstation. In case the OCT acquisition software (ThorImage, Thorlabs Inc.) or the operating system malfunctions, the operator will reboot the system.

Cherry Imaging, Version 19.08.3322 (Yokneam, Israel)

The Cherry Imaging system is a photographic system that captures patient images using standard lighting conditions with no special positioning required. The images are analyzed using Cherry Imaging algorithms to create volumetric images of the photographed area. We expect no device complications or malfunctions due to the Cherry Imaging system.

d. Psychosocial (non-medical) risks

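### The only pre-filler oxytocin sample is tied to cannula placement with no settling interval and no line-only comparator, so changes from baseline may be confounded with a reaction to cannulation, of unknown size and direction.

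*Combined protocol and SAP*

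**What the plan says.** One of the specific aims (section III) is "To evaluate how oxytocin levels change during and after an aesthetic procedure". Section II wants those changes related to satisfaction, and the Video Recording paragraph of VI.d wants the subject's reaction to the mirror correlated with oxytocin.

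Four samples are planned, all at Visit 1. Section VI.a gives the route: "Intravenous access will be placed to facilitate four blood draws to analyze serum oxytocin levels". The Blood Draw paragraph of VI.d gives the sequence:

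- Sample 1, once photography and OCT are done: "before the filler procedure starts, an intravenous access will be placed and approximately 3 cc of blood will be drawn".
- Sample 2: "Immediately after the filler procedure, approximately 3 cc of blood will be drawn".
- Sample 3, at the reveal: "when we show the lips to the subject using a mirror approximately 3 cc of blood will be drawn".
- Sample 4: "30-35 minutes after the filler procedure has been concluded, a final approximate of 3 cc of blood will be drawn".

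Section VIII.a accepts that "The IV access can cause pain during its placement". Subjects with completely inverted lips may go without filler, but for them "the lip filler procedure will be optional and only imaging will be collected in visit 1". Appendix A marks blood draws at Visit 1 only, and screening is by phone or video. Section VII.c plans descriptive statistics on the lips and perioral area and defines no oxytocin change score or test.

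**The concern.** A statement about change during and after a procedure needs a reference sample from before it. Here there is exactly one. It is the only sample listed together with placement of the line, which the protocol accepts can hurt. The other three are listed with no new needle stick.

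If oxytocin reacts to cannulation, that reaction may be present to a different degree in the reference sample than in the samples compared with it. The result would look like an effect of the filler or the reveal. Both age groups follow the same sequence and nobody has a line without filler, so no comparison within the study can remove it. More subjects would not help, because a shared shift does not average out. A purely descriptive analysis does not help either, since the described changes carry the same ambiguity. Once Visit 1 is over, the missing information cannot be recovered.

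**Working it through.** The plan states no figure to reproduce. The target of 40 completers (20 per group, section IV) comes without alpha, power, effect size or SD. The check is therefore of the design, followed by illustrations on stated assumptions.

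**Step 1. Structure, from the documents.**

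| Sample | Timing given | Needle event listed with it | Interval from cannulation |
|---|---|---|---|
| 1 | After imaging, before filler | Line placement | Not stated |
| 2 | Straight after filler | None new for the draw | Not stated |
| 3 | After the reveal; no minutes given | None new | Not stated |
| 4 | 30-35 minutes after filler ends | None new | Not stated |

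Subjects with a line and serial draws but no filler: none.

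**Step 2. Size and sign in general.** Let c be the peak reaction to cannulation, f(t) its time course in minutes from placement, d the delay from placement to sample 1, and x the time from sample 1 to a later sample. Then

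observed change = procedure effect + c × [f(d + x) − f(d)].

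The bracket can be positive, negative or zero. The documents fix none of c, f or d.

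**Step 3. Illustration.** Assume f(t) = (t/5) × exp(1 − t/5), which peaks at 5 minutes, and later samples 15, 20 and 50 minutes after sample 1. For example, with d = 0: f(15) − f(0) = 3 × exp(−2) − 0 = 0.41. With d = 5: f(20) − f(5) = 4 × exp(−3) − 1 = −0.80. Artefact as a share of c:

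| Delay d | Sample 2 − 1 | Sample 3 − 1 | Sample 4 − 1 | Sample 3 − 2 |
|---|---|---|---|---|
| 0 min | +0.41 | +0.20 | 0.00 | −0.21 |
| 1 min | −0.09 | −0.27 | −0.44 | −0.18 |
| 5 min | −0.80 | −0.91 | −1.00 | −0.11 |
| 20 min | −0.18 | −0.19 | −0.20 | −0.01 |
| 30 min | −0.04 | −0.04 | −0.04 | 0.00 |

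The last column is the difference of the first two; for d = 0 it is 0.20 − 0.41 = −0.21. It does not use sample 1, but it can still carry the tail of a reaction if the line was placed shortly before. A settled line shrinks every column.

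**Step 4. Special case on the ratio scale.** Assume the reaction is fully present at sample 1 and gone at every later sample, with no true response. If sample 1 is raised by 5%, 10% or 20%, the apparent ratios are 1/1.05 = 0.952, 1/1.10 = 0.909 and 1/1.20 = 0.833, that is, false falls of 4.8%, 9.1% and 16.7%. If it is lowered by the same amounts, 1/0.95 = 1.053, 1/0.90 = 1.111 and 1/0.80 = 1.250, that is, false rises of 5.3%, 11.1% and 25.0%. The input percentages are assumptions.

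**Step 5. How often an artefact alone would look significant.** The plan has no test, so assume a paired two-sided 5% comparison with an artefact of b SDs of the change: P = Φ(b√n − 1.96) + Φ(−b√n − 1.96).

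| b | n = 20 | n = 40 |
|---|---|---|
| 0.1 | 7.3% | 9.7% |
| 0.2 | 14.5% | 24.4% |
| 0.3 | 26.9% | 47.5% |
| 0.5 | 60.9% | 88.5% |

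The larger sample makes a false signal more likely.

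**The case against.** A reader might infer that every change from baseline contains a needle reaction, in the same direction in every subject. The documents do not support that.

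- They say that placing the line can hurt. They do not say that oxytocin responds.
- They give an order, placement and then draw, not a time. The interval is unspecified; it is not shown to be zero.
- Step 3 shows the sign can differ between later samples. A reaction not yet present at sample 1 and over by sample 4 leaves that last change untouched.

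Nor is there a stated hypothesis linking oxytocin to pain. The only stated hypothesis concerns lip redness, and the oxytocin links are to satisfaction and to the mirror reaction.

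Three further points have weight. Sample 2 follows repeated lip injections, so sample 1 is not the only one near a painful stimulus; but those injections are part of the procedure under study and the cannula is not. No change score is defined, and a constant additive shift would not alter a correlation with the mirror reaction. That protects the correlation only if the reaction is the same in everyone, and it does not help a description of change. Finally, cannulating before imaging would be a poor remedy if unacknowledged: Visit 1 imaging would follow a needle stick and Visit 2 imaging would not.

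These points limit the claim to possible confounding. They do not supply an interval, a second pre-filler sample or a comparator.

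**Conclusion.** The concern holds as a design weakness. The sole reference for the oxytocin aim is tied to cannulation with no stated settling interval, and nothing in the study can separate a reaction to the line from a reaction to the filler or the reveal. Changes from baseline may be confounded, by an amount and in a direction that the documents do not fix and that may differ across the three later samples. Contrasts among those samples are not affected through the baseline.

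The conclusion assumes that one line serves all four draws, as section VI.a intends, and that oxytocin might respond to cannulation, which is a possibility and not a documented fact. The figures in steps 3 to 5 illustrate dependence on the delay and on an assumed reaction; they do not estimate bias in this study. The change is worth making because it is inexpensive and cannot be made afterwards.

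**What to change.** In VI.a and VI.d:

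1. Keep imaging first. Place the line after imaging and draw sample 1 from the settled line, after a fixed rest interval stated in the protocol, just before filler.
2. Record clock times of line placement and of all four draws. This also allows a check of whether the baseline level varies with time since placement.
3. In VII.c, define the oxytocin changes to be described, and report the post-filler to post-reveal contrast alongside them, since it does not use the baseline.
4. State as a limitation that no group has a line without filler.

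The cost is some added time within the 1.5-hour Visit 1; no extra needle, sample or visit is needed. If the line is placed before imaging to save that time, the protocol should acknowledge that the Visit 1 imaging baseline then follows a needle stick while Visit 2 imaging does not.
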